3.11 Discontinuation of the study

The study may be stopped if, in the judgment of sponsor, trial subjects are placed at undue risk because of clinically significant findings that:

- meet individual stopping criteria or are otherwise considered significant
- are assessed as causally related to study drug,
- are not considered to be consistent with continuation of the study

Regardless of the reason for termination, all data available for the subject at the time of discontinuation of follow-up must be recorded in the CRF. All reasons for discontinuation of treatment must be documented. In terminating the study, the Sponsor will ensure that adequate consideration is given to the protection of the subjects' interests.

4. Study plan and timing of procedures

Table 1 Study Plan detailing the procedures

Visit

Visit window

Days -28 to 0 for Visit 1

±0 day for Visit 2

±1 day for Visits 3 and 4

±5 days starting at Visit 5 1

Screening	2	3	4	5	6	7	8 (n)	30-day	follow-up
-----------	---	---	---	---	---	---	-------	--------	-----------

For details see Protocol Section

Week	0	2	4	8	12	16	20+		Section
------	---	---	---	---	----	----	-----	--	---------

Day	-	0	14	28	56	84	112	140+	-
-----	---	---	----	----	----	----	-----	------	---

Written informed consent (including tissue samples, pharmacogenetics) X

Demographics X

Physical examination, height, and weight X
X

Medical/surgical history X

Inclusion/exclusion criteria X

Archival tumor tissue X

12-lead ECG	X	X	X	X	X	X	X	X	X
-------------	---	---	---	---	---	---	---	---	---

Vital signs	X	X	X	X	X	X	X	X	X
-------------	---	---	---	---	---	---	---	---	---

AZD9291 dispense/return		X		X	X	X	X	X	X
-------------------------	--	---	--	---	---	---	---	---	---

Concomitant medication	X	X	X	X	X	X	X	X	X
------------------------	---	---	---	---	---	---	---	---	---

Adverse event review (AEs and SAEs)			X	X	X	X	X	X	X
X	X								

Blood samples for haematology and clinical chemistry			X	X	X	X	X	X	X
--	--	--	---	---	---	---	---	---	---

	X	X	X					
Urinalysis	X	X	X	X	X	X	X	X
Blood sampling for cfDNA			X			X		X

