4.3 Follow-up period

Descriptions of the procedures for this period are included in the Study Plan (Table 1) with exceptions of the following specific requirements for the follow-up period: Patients will return to the clinic/hospital for follow-up assessments 30 days (± 7 days) after their last dose. If a patient discontinues AZD9291, they will also attend a study treatment discontinuation visit.

5. Study assessments

The investigator will ensure that data are recorded on the electronic Case Report Forms (eCRFs) as specified in the study protocol and in accordance with the instructions provided.

The investigator ensures the accuracy, completeness, and timeliness of the data recorded and of the provision of answers to data queries according to the sponsor agreement. The investigator will sign the completed eCRFs. A copy of the completed eCRFs will be archived at the study site.

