6.3 Recording of adverse events

6.3.1 Time period for collection of adverse events

Adverse Events will be collected from time of signature of informed consent, enrolment throughout the treatment period and including the 30-day follow-up period. SAEs will be recorded from the time of informed consent.

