6.3.2 Follow-up of unresolved adverse events

Any AEs that are unresolved at the subject's last visit in the study are followed up by the Investigator for as long as medically indicated, but without further recording in the CRF. The sponsor retains the right to request additional information for any subject with ongoing AE(s)/SAE(s) at the end of the study, if judged necessary.

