6.3.11 Deaths

All deaths that occur during the study, or within the protocol defined 30 day post study follow up period after the administration of the last dose of study treatment, must be reported as follows:

- Death clearly the result of disease progression should be reported to the study monitor at the next monitoring visit and should be documented in the eCRF but should not be reported as an SAE.
- Where death is not due (or not clearly due) to progression of the disease under study, the AE causing the death must be reported to the study monitor as a SAE within 24 hours (see Section 6.3.8 for further details). The report should contain a comment regarding the co involvement of progression of disease, if appropriate, and should assign main and contributory causes of death. This information can be captured in the 'death eCRF'.
- Deaths with an unknown cause should always be reported as a SAE. A post mortem maybe helpful in the assessment of the cause of death, and if performed a copy of the post-mortem results should be forwarded to AstraZeneca within the usual timeframes.

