Non-serious adverse events and SAEs will be collected from the time consent is given, throughout the treatment period and up to and including the 30 day follow-up period. After withdrawal from treatment, subjects must be followed-up for all existing and new AEs for 30 calendar days after the last dose of trial drug and/or until event resolution. All new AEs occurring during that period must be recorded (if SAEs, then they must be reported to the FDA and AstraZeneca). All study-related toxicities/ SAEs must be followed until resolution, unless in the Investigator's opinion, the condition

is unlikely to resolve due to the patient's underlying disease.

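### The closing safety visit may fall up to 7 days before the 30-day event collection period ends, and CRF recording of unresolved events stops at the last study visit although follow-up to resolution is required

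*Combined protocol and SAP*

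**What the plan says.** **Timing of the closing visit.** Section 4.3 asks patients to return for "follow-up assessments 30 days (± 7 days) after their last dose". It also mentions a treatment discontinuation visit, with no timing given. Table 1 in Section 4 ends with a 30-day follow-up column, and its header gives a general tolerance of ± "5 days starting at Visit 5" without saying whether this covers the follow-up column.

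**Collection period.** Section 6.3.1 collects adverse events from consent "throughout the treatment period and including the 30-day follow-up period". Section 6.4 repeats this for serious and non-serious events, adds that after treatment ends "subjects must be followed-up for all existing and new AEs for 30 calendar days after the last" dose and/or until the event resolves, and makes recording of new events in that period mandatory. Section 6.3.11 covers deaths during the study or "within the protocol defined 30 day post study follow up period after the administration of the last dose of study treatment".

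**Events still open.** Under Section 6.3.2, events unresolved at the subject's last study visit are "followed up by the Investigator for as long as medically indicated, but without further recording in the CRF"; the sponsor may ask for more information. Section 6.4 says study-related toxicities and "SAEs must be followed until resolution, unless in the Investigator's opinion" the condition is unlikely to resolve because of the underlying disease. Section 6.3.3 lists stop date and outcome among the variables collected for every adverse event.

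**The concern.** A symmetric tolerance around day 30 lets the visit that should close a 30-day observation period take place inside it. After an early visit, the plan schedules no further safety contact for a patient who has no other study visits. The site is then obliged to record events that it has no planned occasion to ask about.

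The second issue concerns what happens to events open at the end. One section requires follow-up to resolution; another closes the CRF at the last visit. Neither says where an outcome reached in between is entered.

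Safety and tolerability is a secondary objective, reported descriptively in about 30 patients from about 10 sites. One missed event moves an incidence by 1/30, or 3.3 percentage points. Events that led to stopping treatment may well be unresolved at the closing visit, and their eventual outcome is part of any tolerability summary.

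**Working it through.** **Inputs.** Visit at day 30 ± 7 (Section 4.3); possible alternative tolerance ± 5 (Table 1); collection to day 30 after the last dose (Sections 6.3.1, 6.3.11, 6.4); up to 30 patients (Section 8.2).

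**Step 1: permitted visit days.** Section 4.3: 30 − 7 = day 23 to 30 + 7 = day 37. Table 1 tolerance, if it applies: 30 − 5 = day 25 to 30 + 5 = day 35.

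**Step 2: days without scheduled contact.** For a visit on day T, the gap is max(0, 30 − T).

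| Tolerance | Earliest visit | Largest gap | Share of 30 days |
|---|---|---|---|
| ± 7 days (4.3) | day 23 | 7 days (24–30) | 7/30 = 23.3% |
| ± 5 days (Table 1) | day 25 | 5 days (26–30) | 5/30 = 16.7% |

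**Step 3: average gap.** The documents give no distribution of visit dates, so this is an assumption: T is uniform over the permitted window. With ± 7, half of the visits are early and their mean gap is 7/2 = 3.5 days; the rest have no gap. The overall mean is 0.5 × 3.5 = 1.75 days, or 1.75/30 = 5.8% of the period. With ± 5 it is 0.5 × 2.5 = 1.25 days, or 4.2%. The 3.5-day figure (11.7%) describes early visits only and should not be read as the average over all patients. If sites habitually book early, the mean moves towards 7; if they book at or after day 30, it is 0.

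**Step 4: what is and is not lost.** Section 6.4 makes recording of new events mandatory for the 30 days whatever the visit date, and Section 6.3.5 captures spontaneously reported events. Days 24–30 are therefore days without a planned enquiry, not days outside the collection period. No event rate is given for them, so no under-count can be calculated.

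**Step 5: the recording rules side by side.**

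| Question | 6.3.2 | 6.4 |
|---|---|---|
| How long are open events followed? | As long as medically indicated | 30 calendar days and/or to resolution; study-related toxicities/SAEs to resolution, with one exception |
| Entered in the CRF after the last study visit? | No | Not stated |
| Other route | Sponsor may request information | SAE reporting to the drug supplier and the regulator |

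If the last study visit is on day 23, Section 6.3.2 closes the CRF for an open event while the 30 days of Section 6.4 are still running.

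**Step 6: an illustration.** Section 6.7 describes permanent discontinuation when a reaction has not improved after a hold of up to 3 weeks. The follow-up clock starts at the last dose, so after a full 21-day hold a day-23 visit comes 23 − 21 = 2 days after that point. The event may well still be open.

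**The case against.** The strongest reply has several parts, and most of it stands.

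- **The stated period is not shortened.** A reader might infer that safety will be reported on fewer than 30 days. The text does not support this: Section 6.4 keeps the recording duty for the full 30 calendar days.
- **Some patients have later visits.** Section 1.4 (Figure 1 note) keeps patients who stop for reasons other than progression on the tumour assessment schedule. For them the last study visit, which is the cut-off in Section 6.3.2, can come well after the 30-day visit. This stands, although event review at those visits is not spelled out, it does not help patients who stop for progression, and Section 6.7 withdraws from the study some patients whose toxicity has not resolved.
- **Outcomes are not wholly lost.** It would be too strong to say that results of continued follow-up never reach the data. Section 6.3.2 excludes only the CRF and lets the sponsor ask for more, Section 6.4 describes SAE reporting outside the CRF, and Section 9.4 reconciles SAEs with the Patient Safety database. For non-serious related toxicities, however, the only route described is the optional request.
- **On-drug events are not in the gap.** They precede it and are covered by the treatment visits, the discontinuation visit and the closing visit, even if that is early.
- **Deaths are partly protected.** Overall survival is a secondary endpoint, so vital status has to be obtained somehow, though no schedule of survival contacts is described.
- **Differences between sites** in booking habits are possible but are not shown by anything in the documents.

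What the reply leaves untouched is that no safety contact is scheduled after an early visit for patients with no further visits, and that Sections 6.3.2 and 6.4 do not say where a late outcome is recorded.

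**Conclusion.** The point holds as a modest weakness in safety ascertainment and CRF completeness. The last scheduled safety contact may come up to 7 days (23.3%) before collection ends, or 5 days (16.7%) under the Table 1 tolerance. The mean is about 1.75 days (5.8%) if visits are uniform over days 23 to 37, which is an assumption. It could concern any of the up to 30 patients who stop treatment and have no later visit; how many that will be cannot be derived from the documents.

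Separately, the final outcome and stop date of some related events may be missing from the CRF, mainly non-serious ones. The documents do not establish that events will be under-counted, only that a planned occasion to find them is absent. The two-stage design and the primary response analysis are not affected. This is a worthwhile, inexpensive improvement and not a threat to the trial's main conclusion.

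**What to change.** 1. **Section 4.3:** make the visit window one-sided, so that the visit is not held before day 30 after the last dose (for example day 30 to day 37). The event collection period stays at 30 days; onset dates separate events that begin after it. The largest gap then falls from 7 days to 0. If early visits must remain possible, a telephone check of events and vital status on or after day 30 would serve the same purpose, at the price of one added contact.
2. **Table 1:** state the tolerance of the 30-day follow-up column explicitly and make it match Section 4.3.
3. **Sections 6.3.2 and 6.4:** reconcile them so that, for study-related toxicities and SAEs, the final outcome and date are entered in the CRF until resolution or until the event is judged unlikely to resolve, which is the follow-up Section 6.4 already asks for.

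The cost is slightly less flexible scheduling, and CRF pages kept open for a few events after the last visit, with some extra site and data-management work for those. Sample size, type 1 error and power do not change.

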5.1 Efficacy assessments

RECIST 1.1 guidelines for measurable, non-measurable, target lesions (TLs) and non-target lesions (NTLs) and the objective tumour response criteria are present. Baseline CT or MRI assessments of chest and abdomen (including liver and adrenal glands) must be performed no more than 28 days before the start of study treatment, and ideally should be performed as close as possible to the start of study treatment. Additional imaging may be performed based on individual patient signs and symptoms. The methods of assessment used at baseline should be used at each subsequent follow-up assessment. Follow-up assessments should be performed every 2 cycles (\pm 7 days) after the start of treatment until objective disease progression as defined by RECIST 1.1. Any other sites at which new disease is suspected should also be appropriately imaged. If an unscheduled assessment is performed and the patient has not progressed, every attempt should be made to perform subsequent assessments at the scheduled visits whilst the patient remains on study treatment.

Categorisation of objective tumour response assessment will be based on the RECIST 1.1 guidelines for response: CR (complete response), PR (partial response), SD (stable disease) and PD (progression of disease). Target lesion progression will be calculated in comparison to when the tumour burden was at a minimum (i.e. smallest sum of diameters previously recorded on study). In the absence of progression, tumour response (CR, PR, SD) will be calculated in comparison to the baseline tumour measurements obtained before starting treatment. If the investigator is in doubt as to whether progression has occurred, particularly with response to NTLs or the appearance of a new lesion, it is advisable to continue treatment and reassess the patient's status at the next scheduled assessment or sooner if clinically indicated. If repeated scans confirm progression, then the date of the initial scan should be declared as the date of progression. To achieve 'unequivocal progression' on the basis of non-target disease, there must be an overall level of substantial worsening in non-target disease such that, even in presence of SD or PR in target disease, the overall tumour burden has increased sufficiently to merit discontinuation of therapy. A modest 'increase' in the size of one or more NTLs is usually not sufficient to qualify for unequivocal disease progression status. It is important to follow the assessment schedule as closely as possible.

5.2 Safety assessments

5.2.1 Laboratory safety assessments

Blood and urine samples for determination of clinical chemistry, haematology, and urinalysis will be taken at the times indicated in the Study Plan. The date, time of collection and results (values, units and reference ranges) will be recorded on the appropriate eCRF. The clinical chemistry, haematology and urinalysis will be performed at a local laboratory at or near to the Investigator site. Sample

tubes and sample sizes may vary depending on laboratory method used and routine practice at the site.

The following laboratory variables will be measured:

Table 2 Laboratory Safety Variables

Haematology/Haemostasis (whole blood)		Clinical Chemistry (serum or plasma)
B-Haemoglobin (Hb)	S/P-Creatinine	
B-Leukocyte count	S/P-Bilirubin, total	
B-Leukocyte differential count (absolute count)		S/P-Alkaline phosphatase (ALP)
B-Platelet count	S/P-Aspartate transaminase (AST)	
	S/P-Alanine transaminase (ALT)	
Urinalysis (dipstick)	S/P-Albumin	
U-Hb/Erythrocytes/Blood	S/P-Potassium	
U-Protein/Albumin	S/P-Calcium, total	
U-Glucose	S/P-Sodium	
	S/P-Creatine kinase (CK)	

The Investigator should make an assessment of the available results with regard to clinically relevant abnormalities. The laboratory results should be signed and dated and retained at centre as source data for laboratory variables. For information on how AEs based on laboratory tests should be recorded and reported, see Section.

NB. In case a subject shows an AST or ALT $\geq 3 \times \text{ULN}$ or total bilirubin $\geq 2 \times \text{ULN}$ please refer to Appendix C 'Actions required in cases of combined increase of Aminotransferase and Total Bilirubin – Hy's Law', for further instructions.

5.2.2 Physical examination

A physical examination will be performed and include an assessment of the following: general appearance, skin, head and neck (including ears, eyes, nose and throat), respiratory, cardiovascular, abdomen, lymph nodes, thyroid, musculo-skeletal (including spine and extremities) and neurological

systems.

5.2.3 ECG

Patients should be monitored for ECG changes at every cycle. ECGs should be reviewed and any abnormalities noted.

5.2.3.1 Resting 12-lead ECG

Twelve-lead ECGs will be obtained after the patient has been resting semi-supine for at least 10 minutes prior to times indicated. All ECGs should be recorded with the patient in the same physical position. For each time point three ECG recordings should be taken at about 5 minute intervals. A standardised ECG machine should be used and the patient should be examined using the same machine throughout the study if possible.

The investigator or designated physician will review each of the ECGs and may refer to a local cardiologist if appropriate. A paper copy should be filed in the patient's medical records. If an abnormal ECG finding at screening or baseline is considered to be clinically significant by the investigator, it should be reported as a concurrent condition. For all ECGs details of rhythm, ECG intervals and an overall evaluation will be recorded.

5.2.4 Ophthalmologic exam

Full ophthalmic assessment, including slit lamp examination, should be performed at screening and if a patient experiences any visual symptoms (including blurring of vision), with additional tests if clinically indicated. Ophthalmology examination results should be collected in the eCRF.

Any clinically significant findings, including those confirmed by the ophthalmologist must be reported as an AE. Photographs should be performed to record any clinically significant findings. These photographs should be available for submission to AstraZeneca representatives if necessary.

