6.1 Definition of adverse events

An adverse event is the development of an undesirable medical condition or the deterioration of a pre-existing medical condition following or during exposure to a pharmaceutical product, whether or not considered causally related to the product. An undesirable medical condition can be symptoms (e.g., nausea, chest pain), signs (e.g., tachycardia, enlarged liver) or the abnormal results of an investigation (e.g., laboratory findings, electrocardiogram). In clinical studies, an AE can include an undesirable medical condition occurring at any time, including run-in or washout periods, even if no study treatment has been administered. The term AE is used to include both serious and non-serious AEs.

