6.3.6 Adverse events based on examinations and tests

Deterioration as compared to baseline in protocol-mandated laboratory values, vital signs should only be reported as AEs if they fulfil any of the SAE criteria or are the reason for discontinuation of treatment with the investigational product.

If deterioration in a laboratory value/vital sign is associated with clinical signs and symptoms, the sign or symptom will be reported as an AE and the associated laboratory result/vital sign will be considered as additional information. Wherever possible the reporting Investigator uses the clinical, rather than the laboratory term (e.g., anaemia versus low haemoglobin value). In the absence of clinical signs or symptoms, clinically relevant deteriorations in non-mandated parameters should be reported as AE(s). Any new or aggravated clinically relevant abnormal medical finding at a physical examination as compared with the baseline assessment will be reported as an AE.

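### Section 5.2.4 makes clinically significant eye findings AEs with no exception for the pre-dose screening exam, contrary to 5.2.3.1, 6.1 and 6.3.6 (minor)

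*Combined protocol and SAP*

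**What the plan says.** Section 5.2.4 says that a full eye assessment with slit lamp "should be performed at screening and if a patient experiences any visual symptoms". It asks for the results in the eCRF and for photographs of significant findings. On reporting, it says: "Any clinically significant findings, including those confirmed by the ophthalmologist must be reported as an AE". That sentence does not distinguish the screening exam from later ones and does not require a finding to be new or worse.

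Other sections that bear on the same situation:

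- **5.2.3.1 (ECG).** If a screening or baseline abnormality is judged clinically significant, "it should be reported as a concurrent condition".
- **6.1 (AE definition).** An AE is "the development of an undesirable medical condition or the deterioration of a pre-existing medical condition", following or during exposure. The section adds that an AE can arise before any study treatment is given.
- **6.3.6 (examinations and tests).** "Any new or aggravated clinically relevant abnormal medical finding at a physical examination as compared with the baseline assessment will be reported as an AE".
- **6.3.1 (collection window).** "Adverse Events will be collected from time of signature of informed consent". The screening visit in Table 1 (day -28 to day 0) can therefore fall inside the window.
- **2.2 and 8.3.** The safety outcome is AEs and SAEs by CTCAE 4.0. The safety set is everyone who received at least one dose.

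**The concern.** Screening is the only full eye exam that every patient is due to have; later ones depend on visual symptoms. A long-standing eye condition first documented by the slit lamp at screening has neither developed nor deteriorated on study, yet 5.2.4 read literally makes it an AE. The study has one arm, so no control group would show how much eye disease was there already.

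At stake is the ocular part of the safety tabulation. Safety and tolerability is the first-listed secondary objective, and the protocol gives eye events particular attention: 3.8 has contact-lens and eye-drop restrictions, and 3.9 and 6.7.3 have a rule on corneal ulceration. A count that mixes pre-existing disease with on-treatment events is hard to interpret. It is harder still if some of the roughly 10 sites follow 5.2.4 and others follow 6.1.

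**Working it through.** The plan states no figure on this point, so the check is mainly a comparison of text.

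**Step 1. One situation, four rules.** Take a clinically significant abnormality that exists before first dose and does not change.

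| Section | How the abnormality is handled |
|---|---|
| 5.2.3.1, ECG at screening or baseline | Concurrent condition |
| 6.3.6, physical examination | Not an AE: neither new nor aggravated |
| 6.1, general definition | Not an AE: neither a development nor a deterioration |
| 5.2.4, eye exam | AE, on the literal wording |

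Section 5.2.2 includes the eyes in the physical examination. An unchanged eye abnormality is thus not an AE if seen at the physical examination, but is one if seen at the slit lamp.

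**Step 2. Does a later rule remove the entry?**

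- The collection window does not: it opens at consent (6.3.1, repeated in 6.4).
- The safety set does not: 8.3 restricts which patients count, not when an event began. It does exclude findings in screen failures, who are never dosed.
- The outcome definition does not: 2.2 has no treatment-emergent restriction.
- Section 8 does not: it defines no treatment-emergent AE, and 8.1 refers to a SAP only in case one exists.

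**Step 3. Can the entries be identified anyway?** Largely yes. Section 6.3.3 collects start and stop dates and a causality rating for each AE, and 5.2.4 puts the exam results in the eCRF. Dates alone have one weak spot: the screening window runs to day 0, which is also the day of Visit 2, so a screening exam on that day could share its date with the first dose.

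**Step 4. Size.** Input: up to 30 patients dosed (8.2).

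- One patient with such an entry adds at most 1/30 = 3.3 percentage points to the proportion with an ocular AE. It adds nothing if that patient also has an on-treatment ocular AE, because the patient already counts.
- The documents give no prevalence q of clinically significant eye findings at screening. For assumed values, the expected number of patients is 30q and the chance of at least one is 1 − (1 − q)^30:

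| Assumed q | Expected patients, 30q | Chance of at least one |
|---|---|---|
| 2% | 0.6 | 1 − 0.98^30 = 45.5% |
| 5% | 1.5 | 1 − 0.95^30 = 78.5% |
| 10% | 3 | 1 − 0.90^30 = 95.8% |
| 20% | 6 | 1 − 0.80^30 = 99.9% |
| 30% | 9 | 1 − 0.70^30 > 99.9% |

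These rows assume that every site applies 5.2.4 literally and that nobody filters by onset date. They show that the issue could plausibly arise in a study of this size; they do not predict the count.

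**The case against.** The strongest reply is that 5.2.4 should be read with the rest of the protocol. AE is a defined term, and an unchanged pre-existing condition does not meet the definition in 6.1. Section 6.3.6 shows that the protocol's general approach is comparison with baseline. On that reading, 5.2.4 only says that a significant eye finding which is an AE must be reported. The data collected would also let an analyst set pre-dose entries aside, and the effect is confined to one organ class in a descriptive table.

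Much of this stands. It rules out the claim that pre-existing eye disease will certainly be counted at every site. It does not remove the contradiction: 5.2.4 is the specific, mandatory instruction for eye findings, 6.3.6 does not name the slit-lamp exam, and a site could reasonably follow either text. Separation at analysis is possible, but no stated rule requires it.

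A reader might infer two stronger points that the documents do not support:

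- **That baseline eye disease goes unrecorded, so later worsening cannot be told apart from it.** Section 5.2.4 itself puts exam results in the eCRF and asks for photographs, and 6.3.3 collects AE dates. A baseline for comparison exists.
- **That the ocular AE rate would be inflated by a large, known amount, or that screening would supply most ocular AEs.** Suppose 10% to 40% of patients had a screening finding and an independent 10% had a true on-treatment ocular AE. The reported rate would then be 1 − 0.9 × 0.9 = 19% to 1 − 0.9 × 0.6 = 46%. Neither input comes from the documents. At the lower end the two sources are equal, so screening would not supply most of the events.

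**Conclusion.** The point holds as an internal contradiction with a limited effect. Followed literally, 5.2.4 brings pre-existing eye disease into the ocular AE count, against 5.2.3.1, 6.1 and 6.3.6, and nothing in Section 8 takes it out. The likely practical result is either over-counting or reporting that differs between sites. The size is up to 3.3 percentage points per affected patient among 30 dosed; the total cannot be stated because the documents give no prevalence.

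This rests on two assumptions: that at least some sites apply 5.2.4 as written, and that pre-dose entries are not filtered at analysis. Objective response, the two-stage decision rule and the sample size are not touched. Severity: minor.

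**What to change.** - **Section 5.2.4.** State that clinically significant findings at the screening eye exam are recorded as concurrent conditions, as 5.2.3.1 does for ECGs, and that only findings new or worse than the screening exam are reported as AEs. This also settles a screening exam done on day 0, which a date filter alone might not.
- **Section 8.** State that AEs are tabulated if their onset or worsening is on or after the first dose. This closes the same gap for AEs of every type, which the change to 5.2.4 alone would not do.

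The cost is about one sentence in each section and an eCRF completion note. No extra exams, visits or patients are needed, because the screening results and AE dates are already collected.
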